#### 3.1.2. Part 1 – Safety Expansion

Approximately 36 evaluable subjects will be enrolled in the Part 1 safety expansion, and each safety expansion cohort will enroll approximately 9 evaluable subjects. If < 3 of 9 evaluable subjects experience a DLT, then the cohort will be deemed safe. If > 1 safety expansion cohort is deemed safe, then the RP2D and schedule will be determined in conjunction with the investigators and sponsor based on all available safety, PK, results. At the sponsor's discretion, the safety expansion cohorts may be conducted in parallel to Part 2 and may be limited to subjects with specific tumor types to achieve a balance across cohorts.

## 3.1.3. Part 2 – Dose Expansion

Part 2 of the study will further evaluate the safety, tolerability, preliminary efficacy, PK, and pharmacologic activity of the RP2D of INCAGN01876 in subjects with advanced or metastatic adenocarcinoma of the endometrium, melanoma, NSCLC (squamous and nonsquamous), and RCC. Each cohort will comprise an individual tumor type. A Simon 2-stage design (Simon 1989) will be utilized with a stopping rule to allow early termination of a particular cohort at the end of Stage 1 if there are insufficient responses observed. During Stage 1, 9 subjects will be enrolled; if no responses are observed in 16 weeks with 2 scans, then enrollment in the cohort will be terminated. If at least 1 response is observed, then 8 additional subjects will be enrolled into that cohort (Stage 2), for a maximum of 17 subjects per cohort.

Subjects will continue to receive INCAGN01876 until Protocol-defined withdrawal criteria are met. Continuous evaluation of toxicity events will be performed throughout enrollment in Part 2 of the study. If the cumulative incidence of DLTs occurs in > 33% of subjects after 6 subjects are observed for at least 28 days, further enrollment will be interrupted until the sponsor determines the appropriate course of action. All AEs, regardless of the time of occurrence on study, may be considered in determining the appropriate dose, schedule, and MNTD.

Toxicity will continue to be monitored throughout the treatment period. If > 33% of subjects (minimum of 6 subjects) experience a Grade  $\ge 3$  toxicity related to study drug after completing  $\ge 4$  cycles, then the MNTD will be determined in conjunction with the investigators and sponsor based on all available safety data.

### 3.2. Randomization

Not applicable.

## 3.3. Control of Type I Error

All statistical analyses are exploratory in nature. Unless otherwise specified, all CIs provided will be at the 95% confidence level.

## 3.4. Sample Size Considerations

## 3.4.1. Sample Size in Part 1

The primary objective of Part 1 of the study is to determine the MTD or PAD of INCAGN01876. The total number of subjects will depend on the number of dose levels tested before the MTD or PAD is established. Approximately 42 subjects (6 subjects per dose level for 7 dose levels) will be included based on the dose escalation. Dose escalation will follow the 3 + 3 design algorithm. Based on this algorithm, a minimum of 3 evaluable subjects will be enrolled in each cohort beginning with Cohort 1 (0.03 mg/kg; starting dose) and a maximum of 6 evaluable subjects for each cohort. The probability of declaring a dose cohort as safe for various DLT rates in the 3 + 3 and the safety expansion is summarized in Table 2.

Table 2: Probability of Dose Escalation by DLT Rate for 3 + 3 Design and Safety Expansion

|               | Probability of Declaring Dose Cohort as Safe |   |  |
|---------------|--|---|--|
| True DLT Rate | 3+3 Design                                   | In Both 3 + 3 Design and Safety Expansion |  |
| 10%           | 90.6%  | 85.8%                                     |  |
| 20%           | 70.9%  | 52.3%                                     |  |
| 30%           | 49.4%  | 22.9%                                     |  |
| 40%           | 30.9%  | 7.2%                                      |  |
| 50%           | 17.2%  | 1.5%                                      |  |
| 60%           | 8.2%   | 0.2%                                      |  |

For example, if the true DLT rate is 50% at a given dose level, there is a 17.2% chance that the dose would be escalated. Further, if the true DLT rate is 20%, there is a 70.9% chance that the dose would be escalated. If the MTD is not determined at the highest dose level tested during the study, then the MTD is at or above the highest dose level. The MTD is below the lowest dose level of INCAGN01876 if Cohort 1 is not well-tolerated. The PAD may be used in lieu of the MTD and/or prescribed doses may need to be altered in order to determine the MTD.

[figure not shown]
Part 1 of the study may also include safety expansion cohorts evaluating doses and schedules equivalent to or lower than the highest dose levels determined to be safe and/or doses determined to be pharmacologically active. Each safety expansion cohort will enroll 9 evaluable subjects (up to 36 subjects). If < 3 of 9 evaluable subjects experience a DLT, the cohort will be deemed safe. If more than 1 safety expansion cohort is deemed safe, then the RP2D will be determined in conjunction with the investigators and sponsor based on all available safety, PK, results.

#### 3.4.2. Sample Size in Part 2

Part 2 of the study will further evaluate the safety, tolerability, preliminary efficacy, PK, and pharmacologic activity of the RP2D of INCAGN01876. The sample size for each tumor type will be guided by the Simon 2-stage design (Simon 1989). Let  $P_0 = 5\%$  denote a clinically insignificant response rate for all tumor types. In order to determine whether the target response rate (25%) is likely, an initial number of evaluable subjects (9 subjects) treated at the MTD or PAD and schedule of INCAGN01876 will be enrolled in a cohort (Stage 1). If there is no response for the cohort, it will be concluded that the true response rate is unlikely to be greater than or equal to the target rate, and no more subjects will be enrolled in that tumor type in Stage 2.

In the tumor types in which at least 1 response among the Stage 1 subjects is observed, 8 additional evaluable subjects will be treated in Stage 2 to estimate the response rate. At the end of Stage 2, if  $\leq$  2 subjects have responded among the evaluable subjects, the drug will be declared nonpromising for that tumor type. In other words, after the study is finished, if there is a sufficient number of responses in the 2 stages combined, the study compound is considered promising; otherwise it is considered nonpromising. The detailed calculation is based on a 1-sided Type I error of 0.05 and power of 80% for each of the tumor types. Figure 2 shows the power to reject the null hypothesis for various response rates.

Figure 2: Power and Type I Error for Simon 2-Stage Design for Various Response Rates

### 4. DATA HANDLING DEFINITIONS AND CONVENTIONS

# 4.1. Scheduled Study Evaluations and Study Periods

## 4.1.1. Day 1

Day 1 is the date that the first dose of study drug (INCAGN01876) is administered to the subjects.

## **4.1.2. Study Day**

If a visit/reporting date is on or after Day 1, then the study day at the visit/reporting date will be calculated as

Day 
$$\# = (Visit/Reporting Date - Day 1 date + 1).$$

If the visit/reporting date is before Day 1, then the study day at the visit/reporting date will be calculated as

$$Day # = (Visit/Reporting Date - Day 1 date).$$

A study day of -1 indicates 1 day before Day 1.

#### 4.1.3. Baseline Value

Baseline is the last nonmissing measurement obtained before the first administration of INCAGN01876.

When scheduled assessments and unscheduled assessments occur on the same day and time of the assessment or time of first dose is not available, use the following convention to determine baseline:

- If both a scheduled and an unscheduled visit are available on the day of the first dose and the time is missing, use the scheduled assessment as baseline.
- If all scheduled assessments are missing on the day of the first dose and an unscheduled assessment is available, use the unscheduled assessment as baseline.

### 4.1.4. Handling of Missing and Incomplete Data

In general, values for missing data will not be imputed unless methods for handling missing data are specified in this section or relevant sections.

Partial disease/cancer diagnosis date will be handled as follows:

- If only the day is missing, then the imputed day will be the first of the month.
- If both the month and day are missing, then the imputed day and month will be 01 JAN.
- No imputation will be done if the date is completely missing.

Missing or partial date of last dose will be handled as follows:

- If only the day is missing, then the imputed date of the last dose will be the earlier date of the first day of the month or the date that the subject discontinued treatment.
- Otherwise, the date that the subject discontinued treatment will be used as the date of the last dose.

For relevant efficacy endpoints, partial death date will be imputed as follows:

- If mmyyyy for the last contact date = mmyyyy for the death date, then the death date will be set to the day after the last contact date.
- If mmyyyy for the last contact date < mmyyyy for the death date, then the death date will be set to the first day of the death month.
- Otherwise, the partial death date will not be imputed.

For prior and concomitant medications:

The start/stop dates recorded in the CRF by the investigator and his or her research staff will be used to identify when a concomitant medication was taken during the study. Any missing start date must be queried for resolution. Unresolved missing start dates will be handled as follows:

- If the date is completely missing, the medication will be considered both prior and concomitant.
- If only the day is missing, and the last day of the month is before the first dose date on Day 1, then the concomitant medication will be considered as starting before Day 1, and the incomplete date will be imputed as the last day of the month.
- If only the day is missing, and the first day of the month is after the first dose date on Day 1, then the concomitant medication will be considered as starting after Day 1, and the incomplete date will be imputed as the first day of the month.
- If only the day is missing, and the month is equal to the month of the first dose date on Day 1, then the incomplete date will be imputed as the first day of the month.
- If both the month and day are missing, and the last day of the year is before the first dose date on Day 1, then the concomitant medication will be considered as starting before Day 1, and the incomplete date will be imputed as if it is the last day of the year. Otherwise, the incomplete date will be imputed as if it is the first day of the year.

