# **5.2.** Treatment Groups

This is a Phase 1/2, open-label, nonrandomized, multicenter, dose-escalation study. Up to 8 doses will be tested. Data will be summarized overall and by treatment group. Treatment group is defined as the dose regimen initially assigned. Treatment cycles will begin Q14D (± 3 days), but alternate dose schedules (Q21D and/or Q28D) may also be explored due to emerging safety, PK,

- 0.01 mg/kg Q14D
- 0.03 mg/kg Q14D

- 0.1 mg/kg Q14D
- 0.3 mg/kg Q14D
- 1 mg/kg Q14D
- 3 mg/kg Q14D
- 5 mg/kg Q14D
- 10 mg/kg Q14D

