## 6.4. Exposure

For subjects in the FAS population, exposure to INCAGN01876 will be summarized descriptively as the following:

- Total number of infusions: Total number of infusions per subject by the time of date cutoff will be the total number of infusions per subject with a nonzero dose of INCAGN01876.
- **Dose administered per cycle:** The actual dose administered in (mg/kg) per cycle.
- Total dose administered in mg/kg: The total actual dose administered (in mg/kg) across cycles for each subject will be determined according to the following calculation:

For an infusion i, let  $C_i$  be the concentration (in mg/mL) of INCAGN01876 and  $V_i$  be the total volume administered (in mL) reported on the INCAGN01876 dosing CRF; let W be the subject's baseline weight (in kg), and N be the total number of infusions

Total dose administered (in mg/kg) = 
$$\sum_{i=1}^{N} \frac{c_i \times v_i}{w}$$

- Average dose in mg/kg: The average dose (in mg/kg) will be the total dose administered (in mg/kg) divided by the total number of infusions.
- Total dose administered in mg: Total actual dose administered (in mg) across cycles for each subject will be determined according to the following calculation: For an infusion i, let  $C_i$ ,  $V_i$ , and N be defined as above

Total dose administered (in mg) = 
$$\sum_{i=1}^{N} C_i \times V_i$$

• Average dose in mg: The average dose (in mg) will be the total dose administered (in mg) divided by the total number of infusions.

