#### 8.1. General Considerations

Summary tables may be replaced with listings when appropriate. For instance, an AE frequency table may be replaced with a listing if it only contains a few unique PTs reported on relatively few subjects. Data from the Part 1 portion will be summarized separately where appropriate. Additional summaries for specific subgroups may be included on an ad hoc basis.

Unless otherwise stated, table summaries will be limited to AEs occurring within 60 days of the last administration of study drug.

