### 8.2. Adverse Events

#### 8.2.1. Adverse Event Definitions

A TEAE is any AE either reported for the first time or worsening of a pre-existing event after first dose of study drug. Analysis of AEs (as discussed below) will be limited to TEAEs, but data listings will include all AEs regardless of their timing in relation to study drug administration.

Adverse events will be tabulated by MedDRA PT and SOC. Severity of AEs will be graded using the National Cancer Institute CTCAE. The CTCAE version 4.03 is used for this study. The CTCAE reporting guidelines and grading details are available on the Cancer Therapy Evaluation Program website.

The subset of AEs considered by the investigator to be related to study drug will be considered to be treatment-related AEs. If the investigator does not specify the relationship of the AE to study drug, the AE will be considered to be treatment-related. The incidence, frequency, duration, and severity of AEs and treatment-related AEs will be tabulated. In addition, SAEs will also be tabulated.

A grading (severity) scale is provided for each AE term. If the toxicity is not included in the CTCAE v4.03 criteria, it will be rated on a scale of 1 to 4 as follows: 1 = mild, 2 = moderate, 3 = severe, and 4 = life threatening. All toxicities will be graded based on the worst level reached, not the level they may have reached if they had not been treated. When the intensity of an AE changes over time for a reporting period (eg, between visits), each change in intensity will be collected as an AE until the event resolves. Only the worst grade will be reported in AE summaries. Also, the Grade 3 or higher AEs will be reported in a listing.

Any missing onset date, causality, or severity must be queried for resolution. Unresolved missing causality and severity will be handled according to the following rules:

- An unresolved missing causality will be considered treatment-related.
- An unresolved missing severity will be identified as an unknown severity.

For purposes of analysis, all AEs will be considered TEAEs unless the AE can unequivocally be defined as not treatment-emergent.

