[2] The median time and the 95% CI were estimated using Brookmeyer and Crowley.

Abbreviations: CI = confidence interval.

PROTOCOL: INCAGN 1876-101

DRUG/INDICATION: INCAGN01876/Advanced or Metastatic Solid Tumors

TLF VERSION: Draft

(Page n of N)
DATABASE VERSION: XXXXX2016

DATABASE VERSION: XXXXX2016

DATE (TIME): MMDDYYYY (hh:mm)

PROTOCOL: INCAGN 1876-101

DRUG/INDICATION: INCAGN01876/Advanced or Metastatic Solid Tumors

TLF VERSION: Draft

Table 3.1.1.1

Summary of Study Drug Exposure (Population: Part 1 FAS Population)

| Dogo Torrol and Energyoner          | Descriptive Summary          |       |         |           |         |         |       |
|-------------------------------------|------------------------------|-------|---------|-----------|---------|---------|-------|
| Dose Level and Frequency
(mg/kg) | Variable                     | N     | Mean    | STD       | Min     | Median  | Max   |
| Oose 0.01 q14d                      | Number of Treatment Cycles   | XXX X | .xxxx x | . xxxxx x | • XXX X | .xxxx x | • xxx |
|                                     | Duration of Treatment (Days) | XXX   | X.XXXX  | x.xxxx    | X.XXX   | X.XXXX  | X.XXX |
|                                     | Average Dose (mg)            | XXX   | X.XXXX  | x.xxxx    | X.XXX   | X.XXXX  | X.XXX |
|                                     | Average Dose (mg/kg)         | XXX   | x.xxxx  | x.xxxxx   | X.XXX   | x.xxxx  | X.XXX |
| se 0.01 q21d                        | Number of Treatment Cycles   | XXX   | x.xxx   | x.xxxx    | X.XXX   | x.xxxx  | x.xxx |
|                                     | Duration of Treatment (Days) | XXX   | X.XXXX  | x.xxxxx   | x.xxx   | x.xxxx  | X.XXX |
|                                     | Average Dose (mg)            | XXX   | X.XXXX  | x.xxxxx   | x.xxx   | x.xxxx  | x.xxx |
|                                     | Average Dose (mg/kg)         | XXX   | x.xxxx  | x.xxxxx   | x.xxx   | x.xxxx  | x.xxx |

FOLDER\PROGRAM\OUTPUT: XXXXXXXXXXX.SAS\XXXXXX.LST

[a] Duration of treatment (days) = Date of last dose - Date of first dose + 1.

[b] Average dose (mg/kg) = [total actual dose taken (mg/kg) by the subject]/[number of cycles with a nonzero dose]

[c] Average dose (mg) = [total actual dose taken by each subject (mg) in a cycle]/[number of subjects with a nonzero dose in that cycle]

Abbreviations: Min = minimum; Max = maximum; STD = standard deviation.

DATABASE VERSION: XXXXX2016

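### A last-dose date with only the day missing is always set to the 1st of the month, which shortens treatment duration and the 60-day AE table window by about 15 days on average and up to 30

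*SAP*

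**What the plan says.** SAP 4.1.4 has two rules for an incomplete last-dose date.

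- Only the day missing: "the imputed date of the last dose will be the earlier date of the first day of the month" and the treatment discontinuation date. The two candidates are "the first day of the month or the date that the subject discontinued treatment".
- Any other gap: "Otherwise, the date that the subject discontinued treatment will be used as the date of the last dose".

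The last-dose date is used in two places. Footnote a of shell Table 3.1.1.1 (SAP Appendix A) defines "Duration of treatment (days) = Date of last dose - Date of first dose + 1". SAP 8.1 states that, by default, "table summaries will be limited to AEs occurring within 60 days of the last administration of study drug".

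The infusion schedule is in SAP 5.2: "Treatment cycles will begin Q14D (± 3 days), but alternate dose schedules (Q21D and/or Q28D) may also be explored".

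**The concern.** Taking the earlier of two dates is a sensible cap only when one candidate may be too late. Here one candidate is the earliest day of the month and the other cannot precede the true last dose. The discontinuation term therefore never acts, and the rule can only move the last dose backwards. Nothing stops the imputed date from falling before an infusion already on record, or before the first dose.

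The neighbouring rules lean the other way. A date missing in any other manner goes to discontinuation, on or after the true last dose. The partial death date rule in the same section uses the last contact date as a floor when the months match. SAP 8.2.1 treats an AE as treatment-emergent unless it clearly is not.

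At stake are reported treatment duration and the late end of the AE summary tables. AEs are the primary endpoint. Protocol 8.1.2 requires new AEs to be monitored for at least 60 days after the last dose, so events collected as required could drop out of the tables.

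**Working it through.** The plan gives no figure for this rule, so there is nothing to reproduce.

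**Inputs.** The rule is from SAP 4.1.4, cycle lengths of 14, 21 and 28 days from SAP 5.2, the duration formula from shell Table 3.1.1.1, and the 60-day window from SAP 8.1. Assumption: the true last-dose day is uniform over a four-year calendar of 1,461 days. That is 48 months: 28 of 31 days, 16 of 30, 3 of 28 and 1 of 29.

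**Step 1: which term applies.** With discontinuation 0 to 60 days after the last dose, the discontinuation date was earlier than the 1st of the last-dose month in 0 cases. The imputed date is always the 1st.

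**Step 2: days lost.** A true day d loses d − 1 days, so a month of L days contributes L(L − 1)/2.

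- Mean: (28×465 + 16×435 + 3×378 + 1×406)/1,461 = 21,520/1,461 = 14.7 days.
- Maximum: 31 − 1 = 30 days.
- Some loss: (1,461 − 48)/1,461 = 96.7% of cases.

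The 60-day window then ends on average 60 − 14.7 = 45.3 days after the true last dose, and at worst 60 − 30 = 30 days after it.

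**Step 3: conflict with an earlier infusion.** With at least two doses and cycle length c, the previous infusion falls in the same month and after the 1st on L − c − 1 of the L days (0 if negative).

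| Cycle | Days in conflict, of 1,461 | Share |
|---|---|---|
| 14 days | 28×16 + 16×15 + 3×13 + 1×14 = 741 | 50.7% |
| 21 days | 28×9 + 16×8 + 3×6 + 1×7 = 405 | 27.7% |
| 28 days | 28×2 + 16×1 + 0 + 0 = 72 | 4.9% |

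A simulation of 14-day cycles with the ± 3 day window and 2 to 26 doses also gives about 51%. With one dose there is no earlier infusion to contradict.

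**Step 4: zero or negative duration.** In the same simulation, duration is zero or negative in 97% of one-dose subjects with such a date, 51% of two-dose and 6% of three-dose subjects, and in none with four or more doses.

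**Examples.**

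- First infusion 20 April, then 4 May, then an unknown day in May (truly 18 May), discontinued 30 May. The imputed last dose is 1 May, 3 days before the recorded 4 May infusion. Duration is 12 days instead of 29. The AE window ends on 30 June instead of 17 July. Both are 17 days short.
- One dose on 18 May: imputed duration is 1 − 18 + 1 = −16 days.

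**Step 5: month-end in place of the 1st.** The rule becomes the earlier of the last day of the month and discontinuation. If discontinuation is g days after the last dose, the error is +min(L − d, g), never negative. The documents give no value for g. For assumed gaps of 0, 7, 14 and 28 days the mean error is 0, +6.1, +10.6 and +14.7 days.

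**The case against.** The strongest objection is that the rule will hardly ever be used. The drug is infused by site staff on Day 1 of a cycle (protocol 5.2.1). Compliance is calculated from infusion and accountability records (protocol 5.3), accountability records include dates (protocol 10.2), and the last-dose date goes into the eCRF (protocol 5.5.2). The day should normally be recoverable. This stands: the documents give no frequency, but it should be low.

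Some stronger readings are tempting and are not supported.

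- *The imputed date usually contradicts an infusion recorded that month.* It does so in about half of cases on 14-day cycles and in a minority on the longer ones. Counting an infusion on the 1st itself gives 54%, 31% and 8%, but there the two dates agree.
- *Exposure is understated.* SAP 6.4 counts "the total number of infusions per subject with a nonzero dose of INCAGN01876" and sums or averages dose over infusions. None of these uses the last-dose date; only duration of treatment does.
- *AEs vanish from the report.* The cut-off applies to summary tables, and only by default. Under SAP 8.2.1, "data listings will include all AEs regardless of their timing in relation to study drug administration". DLT assessment runs from Cycle 1 Day 1 to Day 28 (protocol 5.4.2) and does not depend on the last dose.
- *Knowing the month gives a worse date than knowing nothing.* That depends on the discontinuation gap. At an assumed 28 days, the fallback errs by +28 days, against a mean of −14.7 under the day-missing rule.

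The month-end rule is also biased, towards a later date. That is true, and it should be stated with the change.

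**Conclusion.** The rule is faulty as written. It always returns the 1st of the month, can produce impossible dates, and errs in one direction only. For an affected subject, it costs 14.7 days on average and up to 30, both in treatment duration and in the 60-day window of the AE summary tables. On 14-day cycles about 51% of imputed dates precede an earlier infusion.

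The averages and shares rest on a uniform day of the month, and the shares also on at least two doses. That the result is always the 1st rests only on discontinuation not preceding the last dose.

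The practical weight is low, since few subjects should have such a date. This is worth correcting but does not threaten the trial's conclusions.

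**What to change.** Replace the day-missing rule in SAP 4.1.4 with: *When the day alone is missing, impute the last-dose date as the earlier of the final day of that month and the date of treatment discontinuation.*

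Neither candidate can precede a recorded infusion or the first dose, so no separate floor is needed. The discontinuation term becomes a working cap, and the direction of error matches the adjacent fallback.

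The cost is one SAP sentence and no new data. The downside to state is a possible overstatement of the last-dose date, which lengthens duration and may admit some AEs from beyond 60 days. In the May example it gives 30 May, 12 days late. For AE capture this is the conservative direction.
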